9.2 Sample Size Determination and Methods

For patients with colorectal adenocarcinoma who have progressed on standard chemotherapy, treatment with either TAS-102 or regorafenib in chemotherapy-refractory patients results in median PFS of approximately 2 months and 6-month PFS of approximately 17%. In phase III trials of nivolumab in chemotherapy-refractory solid tumors (e.g. non-small cell lung cancer [15], urothelial carcinoma [16]) six-month PFS of 30-40% have correlated with an overall survival benefit, as many patients without progression by 6 months will have durable benefit. We therefore would find a 6-month progression-free-survival of 40% to be highly promising in this study population. With 21 evaluable subjects, we will have 81% power to reject a 6-month PFS of 17% (H0) versus 40%, assuming exponential survivorship and using a two sided binomial test with alpha = 0.10.

The primary endpoint of 6-month PFS will be assessed using iRECIST criteria to account for potential pseudoprogression (See Appendix D). If progression is confirmed by imaging (iCPD) or clinically (iUPD without

follow-up imaging), the date of initial progression on imaging (iUPD) will be used. ORR, PFS and DOR will be assessed by both RECIST v. 1.1 and iRECIST and calculated with 90% confidence intervals. PFS at 6 months will be estimated as a crude rate with a 90% CI. Kaplan Meier methods will be used to estimate the survival curves for PFS and OS. ORR will be summarized as a binomial proportion. Median PFS, OS, and DOR will be calculated with 90% confidence intervals.

Analysis of T-cell function, TCR sequencing, and circulating tumor materials will be an exploratory and hypothesis-generating analysis of potential biomarkers. Immune assays in tissue and blood will seek to demonstrate immune activation, generate potential biomarkers to predict response and identify responding T-cell populations and their respective target(s). Circulating tumor measurements will seek to improve upon measurability of response and generate potential genomic biomarkers of response. Logistic regression will be used to evaluate any association of response status and PFS6 with marker, and markers will be summarized by response status and PFS6. Cox regression will be used to test any association between a time-to-event outcome (PFS, OS) and marker expression. Other analyses will be descriptive.

10.0 Safety and Adverse Events

10.1 Definitions

10.1.1 Unanticipated Problems Involving Risk to Subjects or others

Any incident, experience, or outcome that meets all of the following criteria:

- Unexpected in nature, severity, or frequency (i.e. not described in study-related documents such as the IRB-approved protocol or consent form, the investigators brochure, etc)
- Related or possibly related to participation in the research (i.e. possibly related means there is a reasonable possibility that the incident experience, or outcome may have been caused by the procedures involved in the research)
- Suggests that the research places subjects or others at greater risk of harm (including physical, psychological, economic, or social harm).

10.1.2 Adverse Event

An **adverse event** (AE) is any unfavorable symptom, sign, illness or experience that occurs at any dose and develops or worsens in severity during the course of the study. Intercurrent illnesses or injuries should be regarded as adverse events. Abnormal results of diagnostic procedures are considered to be adverse events if the abnormality:

- results in study withdrawal
- is associated with a serious adverse event
- is associated with clinical signs or symptoms
- leads to additional treatment or to further diagnostic tests
- is considered by the investigator to be of clinical significance

10.1.3 Adverse Events of Special Interest

AESIs (serious or non-serious) are defined as AEs of scientific and medical concern specific to the investigational product or program, for which ongoing monitoring and rapid communication by the Principal Investigator to drug manufacturer can be appropriate. Such an event might warrant further investigation in order to characterize and understand it. Depending on the nature of the event, rapid communication by the Principal Investigator to other parties (eg, regulators) might also be warranted.

Details on currently agreed list of AESIs for investigational agents can be found in the current IB. These AESIs are to be reported to drug manufacturer expeditiously within 1 business day of knowledge of the event, during the study through 100 days after receiving the last dose of study treatment, according to the procedures below

10.1.4 Serious Adverse Event

Adverse events are classified as serious or non-serious. A serious adverse event is any AE, that is:

- fatal
- life-threatening
- requires or prolongs hospital stay
- results in persistent or significant disability or incapacity
- a congenital anomaly or birth defect
- an important medical event
- suspected transmission of an infectious agent (eg, pathogenic or nonpathogenic) via the study drug is an SAE
- all occurrences of potential drug-induced liver injury (DILI), meeting the defined criteria below, must be reported as SAEs

Potential drug induced liver injury is defined as:

1) AT (ALT or AST) elevation > 3 times upper limit of normal (ULN)

AND

2) Total bilirubin > 2 times ULN, without initial findings of cholestasis (elevated serum alkaline phosphatase)

AND

3) No other immediately apparent possible causes of AT elevation and hyperbilirubinemia, including, but not limited to, viral hepatitis, pre-existing chronic or acute liver disease, or the administration of other drug(s) known to be hepatotoxic.

All Serious Adverse Events or pregnancies that occur following the subject's written consent to participate in the study through 100 days of discontinuation of dosing must be reported to BMS Worldwide Safety, whether related or not related to study drug, within 1 business day of becoming aware of the event. A Medwatch form will be used to report SAEs to BMS.

All SAEs should be faxed or e-mailed to BMS at:

Global Pharmacovigilance & Epidemiology

Bristol-Myers Squibb Company

[contact]

SAE Email Address: [contact]

Important medical events are those that may not be immediately life threatening, but are clearly of major clinical significance. They may jeopardize the subject, and may require intervention to prevent one of the other serious outcomes noted above. For example, drug overdose or abuse, a seizure that did not result in in-patient hospitalization, or intensive treatment of bronchospasm in an emergency department would typically be considered serious.

All adverse events that do not meet any of the criteria for serious should be regarded as **non-serious adverse events**.

Events or Outcomes Not Qualifying as Serious Adverse Events

The following are not considered SAEs and therefore do not need to be reported as such:

- Pre-planned or elective hospitalization including social and/ or convenience situations (eg, respite care)
- Hospital visits of less than 24 hours duration (eg, patient presents to the emergency room, but is not admitted to a ward)
- Overdose of study drugs or concomitant medication unless the event meets SAE criteria (eg, hospitalization). However, the event should still be captured as a nonserious AE
- Events of progression of the patient's underlying cancer as well as events clearly related to progression of the patient's cancer (signs and symptoms of progression) should not be reported as a serious adverse event unless the outcome is fatal within the safety reporting period. If the event has a fatal outcome within the safety reporting period, then the event of Progression of Disease must be recorded as an AE and as a SAE with CTC Grade 5 (fatal outcome) indicated.

10.2 Adverse Event Reporting Period

The study period during which adverse events must be reported is normally defined as the period from the initiation of any study procedures to the end of the study treatment follow-up. For this study, the study treatment follow-up is defined as 100 days following the last administration of study treatment.

10.3 Preexisting Condition

A preexisting condition is one that is present at the start of the study. A preexisting condition should be recorded as an AE if the frequency, intensity, or the character of the condition worsens during the study period

10.4 General Physical Examination Finding

At screening, any clinically significant abnormality should be recorded as a preexisting condition. At the end of the study, any new clinically significant findings/abnormalities that meet the definition of an AE must also be recorded and documented as an AE.

10.5 Post-Study Adverse Event

All unresolved AEs should be followed by the investigator until the events are resolved, the subject is lost to follow-up, or the AE is otherwise explained. At the last scheduled visit, the investigator should instruct each subject to report any subsequent event(s) that the subject, or the subject's personal physician, believes might reasonably be related to participation in this study. The investigator should notify the Principal Investigator of any death or AE occurring at any time after a subject has discontinued or terminated study participation that may reasonably be related to this study. The Principal Investigator should also be notified if the investigator should become aware of the development of cancer or of a congenital anomaly in a subsequently conceived offspring of a subject that has participated in this study.

Version: 11/24/2020

CONFIDENTIAL

This material is the property of the University of Pennsylvania

10.6 Abnormal Laboratory Values

An abnormal laboratory value that is not already associated with an AE is to be recorded as an AE only if any one of the following criteria is met:

- an action on the study drug is made as a result of the abnormality
- intervention for management of the abnormality is required
- at the discretion of the investigator should the abnormality be deemed clinically significant

10.7 Hospitalization, Prolonged Hospitalization or Surgery

Any AE that results in hospitalization or prolonged hospitalization should be documented and reported as an SAE unless specifically instructed otherwise in this protocol. Any condition responsible for surgery should be documented as an AE if the condition meets the criteria for an AE.

Neither the condition, hospitalization, prolonged hospitalization, nor surgery are reported as an AE in the following circumstances:

Hospitalization or prolonged hospitalization for diagnostic or elective surgical procedures for a preexisting condition. Surgery should not be reported as an outcome of an AE if the purpose of the surgery was elective or diagnostic and the outcome was uneventful.

Hospitalization or prolonged hospitalization required to allow efficacy measurement for the study.

Hospitalization or prolonged hospitalization for therapy of the target disease of the study, unless it is a worsening or increase in frequency of hospital admissions as judged by the clinical investigator.

10.8 Recording of Adverse Events

At each contact with the subject, the investigator must seek information on adverse events by specific questioning and, as appropriate, by examination. Information on all adverse events should be recorded immediately in the source document, and also in the appropriate adverse event module of the case report form (CRF). All clearly related signs, symptoms, and abnormal diagnostic procedures results should be recorded in the source document, though should be grouped under one diagnosis. All adverse events occurring during the study period must be recorded. The clinical course of each event should be followed until resolution, stabilization, or until it has been determined that the study treatment or participation is not the cause. Serious adverse events that are still ongoing at the end of the study period must be followed up to determine the final outcome. Any serious adverse event that occurs after the study period and is considered to be possibly related to the study treatment or study participation should be recorded and reported immediately.

10.9 Stopping Rule for Adverse Events

Bayesian toxicity monitoring with a target treatment discontinuation rate (both ipilimumab and nivolumab discontinued) of 30% will be implemented as outlined in the statistical plan. If the posterior probability that the treatment discontinuation rate due to toxicity exceeds 30%, the Abramson Cancer Center Data Safety Monitoring Committee will be notified and may decide to terminate the study for toxicity.

10.10 Reporting of Adverse Events

Investigators must conform to the AE reporting timelines, formats and requirements of the various entities to which they are responsible, but at a minimum those events that must be reported are those that are:

Version: 11/24/2020

CONFIDENTIAL

This material is the property of the University of Pennsylvania

- Related to study participation,
- Unexpected, and
- Serious or involve risks to subjects or others

If the AE meets institutional reporting criteria, the event will be reported to their IRB. An event may qualify for expedited reporting to regulatory authorities if it is a suspected unexpected serious adverse reaction (SUSAR) in line with relevant regulations.

If the report is supplied as a narrative, the minimum necessary information to be provided at the time of the initial report includes:

- Study identifier
- Study center
- Subject number
- Investigational study product
- A description of the event
- Date of onset
- Current status
- Whether study treatment was discontinued
- The reason why the event is classified as serious
- Investigator assessment of the association between the event and study treatment.

10.10.1 Investigator Reporting: Notifying Drug Manufacturer

All SAEs, AESIs, and pregnancies, regardless of relationship to study drug, must be reported to the drug manufacturer during the study through 100 days after receiving the last dose of study treatment, according to the procedures below. After the specified window, only SAEs considered to be treatment related and all AESIs, regardless of treatment relationship, should be reported. It is important that the investigator provide an assessment of relationship of the SAE or AESI to study treatment at the time of the initial report.

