4.2 Exclusion Criteria

1. Bowel obstruction within the past 60 days

Version: 11/24/2020

CONFIDENTIAL

This material is the property of the University of Pennsylvania

2. Subjects who are currently pregnant, planning to become pregnant, or breast-feeding.
 - a. *Females participants of child-bearing potential are required to use an effective contraception method (see Appendix A) or abstain from intercourse during treatment and for at least 5 months following the last dose*
 - b. *Males participants with partners of child-bearing potential are required to use an effective contraception method (see Appendix A) or abstain from intercourse during treatment and for at least 7 months following the last dose*
3. Subjects who, in the opinion of the physician, would not be clinically appropriate for receipt of the therapy regimen associated with participation
4. Subjects with contraindications to immune checkpoint therapy, as follows:
 - a. Interstitial lung disease that is symptomatic or may interfere with the detection and management of suspected drug-related pulmonary toxicity
 - b. Prior organ allograft or allogeneic bone marrow transplantation
 - c. Pre-existing thyroid abnormality with thyroid function that cannot be maintained in the normal range with medication
 - d. Active autoimmune disease, except for vitiligo, type 1 diabetes mellitus, asthma, atopic dermatitis, or endocrinopathies manageable by hormone replacement; other autoimmune conditions may be allowable at the discretion of the principal investigator
 - e. Condition requiring systemic treatment with corticosteroids
 - Systemic steroids at physiologic doses (equivalent to dose of oral prednisone 10 mg) are permitted.
 - Intranasal, inhaled, topical, intra-articular, and ocular corticosteroids with minimal systemic absorption are permitted.
5. Established non-peritoneal metastatic disease, including but not limited to metastases to the liver, lung, brain, extra-abdominal lymph nodes, and bone
6. A second primary malignancy that, in the judgment of the investigator, may affect interpretation of results
7. Prior treatment with an anti-PD-1, anti-PD-L1, or anti-CTLA-4 antibody
8. Toxicities attributed to prior anti-cancer therapy other than alopecia, fatigue, and peripheral neuropathy must have resolved to Grade 1 or baseline before administration of study drug. In addition, a washout period will be required for prior therapies as specified:
 - a. No chemotherapy within 14 days prior to first dose

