⁹Research blood is to be drawn on the same day as the tumor biopsies during screening and cycle 1 days 10-14. It should not be drawn at the initial screening visit. If the biopsy is omitted, research blood draw is still required and can occur during screening window or on cycle 1 day 1 prior to treatment. Research blood can be drawn within 3 days before or after biopsy if required for scheduling.

Appendix A: Definition of Non-Childbearing Potential and Medically Acceptable Methods of Birth Control

Non-childbearing potential is defined as any of the following (by other than medical reasons):

1. ≥ 45 years of age and has not had menses for >2 years
2. Amenorrheic for <2 years without a hysterectomy and oophorectomy and a follicle-stimulating hormone value in the postmenopausal range upon pre-study (screening) evaluation
3. Post hysterectomy, oophorectomy or tubal ligation. Documented hysterectomy or oophorectomy must be confirmed with medical records of the actual procedure or confirmed by imaging. Tubal ligation must be confirmed with medical records of the actual procedure otherwise the patient must be willing to use 2 other adequate methods.

Females:

Women of child-bearing potential must agree to use 2 of the following forms of contraception OR completely refrain from intercourse during the study and for at least 5 months following the last dose of study drug.

Males:

Men with partners of child-bearing potential must agree along with their partner to use 2 of the following forms of contraception OR completely refrain from intercourse during the study and for at least 7 months following the last dose of study drug.

Acceptable methods include:

- Condoms
- Diaphragm
- Cervical cap
- Intra-uterine device
- Surgical sterilization (tubal ligation or vasectomy)
- Oral contraceptives

Abstinence at certain times of the cycle, such as during ovulation or after ovulation, or withdrawal are not acceptable methods. The list of methods above is not exhaustive and additional contraception methods may also be acceptable. The study doctor must approve the contraceptive methods in subjects with child-bearing potential.

[figure not shown]

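### Mandatory pregnancy reporting to the manufacturer ends 100 days after the last dose, before the protocol's own 5- and 7-month contraception periods end

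*Combined protocol and SAP*

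**What the plan says.** **Reporting.** Section 10.1.4 starts the duty to report SAEs and pregnancies at written consent and ends it 100 days after dosing stops: "through 100 days of discontinuation of dosing must be reported to BMS Worldwide Safety, whether related or not related to study drug". Section 10.10.1 repeats that limit: "All SAEs, AESIs, and pregnancies, regardless of relationship to study drug, must be reported to the drug manufacturer during the study through 100 days" after the last dose. It then states what remains reportable: "After the specified window, only SAEs considered to be treatment related and all AESIs, regardless of treatment relationship, should be reported". Pregnancies are named in the first of these two sentences of 10.10.1 and not in the second. Section 10.2 uses the same length for adverse events in general: "the study treatment follow-up is defined as 100 days following the last administration of study treatment".

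**Contraception.** Section 4.2 asks women of child-bearing potential to use effective contraception or "abstain from intercourse during treatment and for at least 5 months following the last dose". For men with partners of child-bearing potential the period is at least 7 months. Appendix A repeats both; for men, the alternative to contraception is to "completely refrain from intercourse during the study and for at least 7 months following the last dose of study drug". Footnote 5 of the Schedule of Events gives the same 5 and 7 months.

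**After the End of Study visit.** Section 7.3 and footnote 6 of the Schedule of Events limit follow-up to survival and recurrence, taken from the medical record. The last protocol pregnancy test is at the End of Study visit.

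**The concern.** The protocol asks subjects to avoid conception for 5 or 7 months after the last dose, so it treats a pregnancy in that time as something to prevent. Its duty to tell the manufacturer about a pregnancy ends earlier, and no reason is given for the difference. A conception on day 130 in a female subject, or in month 6 in a male subject's partner, falls within the contraception period but outside the reporting window.

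What is at stake is safety information. The pregnancies that the contraception rule is meant to prevent could occur without the manufacturer being told, and nothing in the later follow-up looks for them. The reporting sections also do not say whether a partner's pregnancy counts, although the 7-month rule is written only for men with partners who could conceive. The primary endpoint, power and type I error are not involved.

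**Working it through.** The plan gives no figure of its own to reproduce. The check compares durations.

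**Inputs**
- Reporting window after the last dose: 100 days (10.1.4, 10.10.1).
- Contraception after the last dose: at least 5 months for women and 7 months for men (4.2, Schedule of Events footnote 5, Appendix A).
- Assumptions: a month is 30.4375 days (365.25 / 12), varied below, and a pregnancy is dated by conception.

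**Formulas:** uncovered days = months × days per month − 100; share = uncovered days / post-dose contraception days.

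- Women: 5 × 30.4375 = 152.2 days; 152.2 − 100 = 52.2 days; 52.2 / 152.2 = 34%.
- Men: 7 × 30.4375 = 213.1 days; 213.1 − 100 = 113.1 days; 113.1 / 213.1 = 53%.
- In months, the reporting window is 100 / 30.4375 = 3.29.

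**Sensitivity to how a month is counted**

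| Month | Women: period, gap | Men: period, gap |
|---|---|---|
| Calendar months, every start date over four years | 150–153 days, 50–53 days | 212–215 days, 112–115 days |
| 28 days | 140 days, 40 days | 196 days, 96 days |

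The gap remains under every convention.

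**Sensitivity to the denominator.** The 34% and 53% refer to the post-dose part only. Contraception is also required during treatment, when pregnancies are fully reportable. Adding the time from first to last dose lowers the share:

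- 56 days on treatment (illustrative): 52 / (152 + 56) = 52 / 208 = 25% for women; 113 / (213 + 56) = 113 / 269 = 42% for men.
- About 24 months, the maximum (24 × 30.4375 = 730.5 days): 52.2 / 882.7 = 6% for women; 113.1 / 943.6 = 12% for men.

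The number of uncovered days is the same in each case. All of these are shares of time, not of expected pregnancies.

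**Other routes that could bring a later pregnancy to notice**

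| Section | What it requires | Would it capture an uncomplicated pregnancy? |
|---|---|---|
| 10.5 | At the last scheduled visit, subjects are told to report later events thought to be related; the Principal Investigator is told of possibly related deaths or AEs at any time, and of cancer or a congenital anomaly in later-conceived offspring if it becomes known | Not required |
| 10.1.4 with 10.8 and 10.10.1 | A congenital anomaly is an SAE, so it stays reportable late if judged related | No; only that outcome |
| 10.10.2 | The IRB is told of unexpected, related AEs during or after the study, and of violations that raised risk | Only on a judgement of relatedness or risk |
| 10.10.3 | A deviation goes to the DSMC and IRB within 10 days if it raised risk, could recur or could amount to noncompliance | Only if classed that way; not a report to the manufacturer |

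None of these is a rule for pregnancies as such.

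**The case against.** The best case for the present text is that 100 days is used consistently in 10.1.4, 10.2 and 10.10.1, and that nothing in the protocol says the reporting window must match the contraception period. A contraception period may reasonably include a margin of caution that a reporting window does not. The trial has 21 pretreated subjects with metastatic disease, the number able to conceive or father a child is not stated, and few pregnancies are likely. All of this stands, and it limits the weight of the point. It does not explain why reporting stops at 100 days when the precaution continues.

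Three stronger readings are tempting, and the documents do not support them.

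- **A reader might infer that a pregnancy after day 100 triggers no report at all.** If the conception breaches the contraception rule, the deviation provisions of 10.10.2 and 10.10.3 may apply. Section 10.5 also has subjects told to report later events they think related, and related SAEs remain reportable. These routes are conditional, and the deviation and IRB routes do not run to the manufacturer, but they exist.
- **A reader might infer that partner pregnancies are excluded.** Sections 10.1.4 and 10.10.1 say pregnancies without restricting the word to female subjects. Their status is unaddressed, and the consent pages, which might address it, are not available.
- **A reader might infer that every such pregnancy is itself a serious event.** Section 10.1.4 does not list pregnancy among the SAE criteria; it lists a congenital anomaly or birth defect.

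One point cannot be settled. The AESI list is in the investigator brochure, which is not among the documents. If it included pregnancy, 10.10.1 would keep pregnancies reportable after the window. Section 10.10.1 does name pregnancies separately from AESIs, which suggests that they are a separate category.

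**Conclusion.** The point holds as a gap in safety reporting. About 52 post-dose days for women (range 50–53 by calendar) and 113 for men (112–115) lie inside the protocol's contraception period and outside its only mandatory pregnancy report to the manufacturer. That is 34% and 53% of the post-dose period. These shares should not be read as shares of the whole contraception period, which includes time on treatment; on that basis they are smaller and depend on how long the subject was treated.

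The conclusion assumes that the AESI list does not include pregnancy and that no document outside this set sets a longer window. No view is taken on whether 100 days, 5 months or 7 months is the right length; the finding is that the sections do not agree and give no reason. Expected events are few and no efficacy conclusion changes, so this is an inexpensive improvement and no threat to the trial's validity.

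**What to change.** Reconcile 10.1.4 and 10.10.1 with 4.2, footnote 5 of the Schedule of Events and Appendix A:

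1. Separate pregnancy from the 100-day SAE and AESI window. Keep the start at written consent, as 10.1.4 has it, so that pregnancies arising in screening stay covered. Move only the end, to the close of the post-dose contraception period already stated for that subject. Leave the 100-day window for other events unchanged.
2. Amend the sentence in 10.10.1 on reports after the window so that it no longer drops pregnancies.
3. State that pregnancies in male subjects' partners are included, with the partner's consent.
4. Add pregnancy to the instruction that 10.5 already requires at the last scheduled visit.

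If the shorter window is intended, the protocol should say so and give the reason.

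**Cost.** A few sentences in an amendment, a longer reporting window for a rare event, and a short partner consent form. No added visits or tests are needed. Following a pregnancy to its outcome would be a further choice, and would need some contact beyond the record review described in footnote 6 of the Schedule of Events.
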